#### D. Vaccine preparation and administration

Vials will be thawed, and the plasmid DNA will be used by itself or will be used to reconstitute the GM-CSF, on the day of administration. Specifically:

For each of the immunizations: 0.25 mL of 0.2 mg/mL pTVG-HP will be drawn into each of two tuberculin syringes. This effectively provides a 100- $\mu$ g dose of DNA. If GM-CSF is used as an adjuvant, 0.6 mL of 0.2 mg/mL pTVG-HP will be withdrawn and used to reconstitute 250  $\mu$ g GM-CSF. 0.25 mL will then be drawn into each of two tuberculin syringes. This effectively provides a 100- $\mu$ g dose of DNA and 208  $\mu$ g GM-CSF.

The vaccine with or without GM-CSF will then be administered intradermally on the deltoid area of the lateral aspect of the arm (left arm, preferentially) in two adjacent sites, with the total syringe contents (0.25 mL) administered at each site.

### 5. Patient Selection

#### A. Inclusion Criteria

1. Patients must be at least 18 years of age with a histologic diagnosis of adenocarcinoma of the prostate
2. Patients must have undergone radical prostatectomy
3. Patients must have completed local therapy by surgery and any adjuvant/salvage radiation therapy at least 3 months prior to entry, with removal or ablation of all visible disease, including seminal vesical and/or local lymph node involvement.

4. Patients must have biochemically recurrent, non-metastatic (by CT and bone scan) clinical stage D0/M0 disease defined by the following:
  - Patients must have evidence of detectable serum PSA with at least 4 serum PSA measurements available, from the same clinical laboratory, at least two weeks apart up to one year, and the final serum PSA value must be  $\geq 2.0$  ng/mL.
  - PSA doubling time, calculated from most recent 4 serum PSA values (collected up to one year prior to enrollment, at least 2 weeks apart, and all from the same clinical laboratory), must be a positive number (i.e. evidence of PSA rise over time).
  - PSA doubling time will be calculated using the Memorial Sloan-Kettering Cancer Center nomogram:  
(<http://www.mskcc.org/applications/nomograms/prostate/PsaDoublingTime.aspx>).
  - Patients must not have definitive evidence of metastases as determined by CT of the abdomen/pelvis and bone scintigraphy (bone scan). Note: patients with lesions detectable by highly sensitive methods (e.g. NaF PET imaging or PSMA PET imaging) will be considered eligible as long as these lesions do not meet size criteria on CT imaging (visceral lesions suspicious for metastases or lymph node  $> 15$  mm in short axis) and/or are not independently observed on bone scan.
5. Patients with a prior history of a second malignancy are eligible provided they have been treated with curative intent and have been free of disease greater than three years. There will be no exclusion for patients with a history of basal cell carcinoma, squamous cell skin cancer, superficial bladder cancer, or other *in situ* carcinoma that has been adequately treated.
6. Patients who are sexually active must use a reliable form of contraception while on study and for 4 weeks after the last immunization.
7. ECOG performance score  $< 2$  and life expectancy of at least 12 months.
8. Patients must have normal hematologic, renal and liver function as defined by: WBC  $\geq 3000/\text{mm}^3$ , hematocrit  $\geq 30\%$ , platelet count  $\geq 100,000/\text{mm}^3$ , serum creatinine  $\leq 1.5$  mg/dl or a calculated creatinine clearance  $\geq 60$  cc/min, AST or ALT  $< 3.0 \times \text{ULN}$ , and serum bilirubin  $\leq 2.0$  mg/dl (except participants with Gilbert Syndrome, who can have total bilirubin  $< 3.0$  mg/dL), within 4 weeks prior to first immunization.
9. Patients must be informed of the experimental nature of the study and its potential risks and must sign an IRB-approved written informed consent form indicating such an understanding.
10. Willingness to provide blood samples for immune studies, per study calendar, up to one year after study, even if off study treatment.

B. Exclusion Criteria

1. Small cell or other variant prostate cancer histology
2. Patients cannot have evidence of immunosuppression or have been treated with immunosuppressive therapy, such as chemotherapy or chronic treatment dose corticosteroids (greater than the equivalent of 10 mg prednisone per day), within 3 months of the first vaccination.

3. Seropositive for HIV, hepatitis B (HBV) or hepatitis C (HCV) per patient history due to the immunosuppressive features of these diseases.
4. Prior treatment with an LHRH agonist or nonsteroidal antiandrogen, except in the following circumstances: Neoadjuvant/adjuvant androgen deprivation therapy administered with radiation therapy or at the time of prostatectomy is acceptable, provided that there was no evidence of PSA progression while on treatment. In this situation, patients must not have received more than 24 months of androgen deprivation treatment. Other treatment with androgen deprivation therapy is prohibited.
5. Serum testosterone at screening < 50 ng/dL.
6. Patients must not be concurrently taking other medications or supplements with known hormonal effects, including PC-SPES, megestrol acetate, finasteride, ketoconazole, estradiol, or Saw Palmetto. All other medications with possible anti-cancer effects must be discussed with the PI prior to study entry.
7. Patients previously treated with herbal supplements as described in 5.B.6 or other potential or experimental therapies for prostate cancer must have discontinued these treatments and completed at least a 4 week washout prior to beginning treatment.
8. Patients must not have evidence of bone metastases or lymph node involvement as determined by bone scan or CT scan of the abdomen and pelvis within 4 weeks of study registration. Note: Advanced imaging modalities (such as NaF-PET/CT, choline PET/CT, fluviclovine, or PSMA PET scans) will NOT be used to determine evidence of metastases for eligibility purposes or for defining disease progression.
9. Patients must not have been treated with a prior DNA vaccine therapy for prostate cancer.
10. Patients must not have known psychological or sociological conditions, addictive disorders or family problems, which would preclude compliance with the protocol.
11. Patients must not have known allergic reactions to GM-CSF.
12. Patients with unstable or severe intercurrent medical conditions or laboratory abnormalities that would impart, in the judgment of the PI, excess risk associated with study participation or study agent administration.
13. Patients cannot have concurrent enrollment on other phase I, II, or III investigational therapeutic treatment studies.

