#### B. Endpoints

The primary endpoints for the trial will be safety, tolerability, and PSA complete response (PSA CR) rate. A PSA CR will be defined as a serum PSA <0.2 ng/mL, with a confirmatory PSA <0.2 ng/mL at least 4 weeks later, as per PCWG2 recommendations [67]. To qualify as a PSA CR, there must be no evidence of radiographic progression. Patients will come off study at the time of appearance of metastatic disease (radiographic progression), at the time of undue toxicity (as defined below), or at the discretion of the patient and treating physician that other therapies for

prostate cancer are warranted. Patients should be discouraged from discontinuing protocol treatment for PSA rise only. Patients will continue to have blood drawn for immune studies, as per study calendar, up to one year after screening, even if off study prior to that time.

All subjects will undergo radiographic imaging (CT of abdomen and pelvis and bone scan) prior to treatment, and at 6-month intervals (or as clinically indicated). The appearance of lesions consistent with metastatic disease will be used to define radiographic progression, and from these the 2-year metastatic progression-free survival will be calculated for each treatment arm, as well as the median progression-free survival. NOTE: Lesions detected by F-NaF-PET/CT or other advanced imaging (such as NaF-PET/CT, choline PET/CT, fluviclovine, or PSMA PET scans) only will not be used to define metastatic disease or disease progression. MRI imaging may substitute for CT, but the same type of imaging must be used to determine eligibility and progression. RECIST 1.1 criteria will be used to define metastatic disease (appearance of a visceral lesion > 10 mm by CT or MRI, lymph node > 15 mm in short axis, or appearance of new lesions on bone scan consistent with metastatic disease). The 2-year metastasis-free survival will be determined by investigator review of radiographic studies (CT/MRI and bone scintigraphy) performed 2 years after study initiation in subjects who have not already met criteria for radiographic progression.

PSA doubling times will be calculated from four available serum PSA values obtained up to one year from the same clinical laboratory prior to study enrollment, up to and including the baseline value, and used to determine a pre-treatment PSA doubling time (PSADT). Similarly, a post-treatment doubling time will be calculated from:

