#### C. Serum PSA Doubling Time Evaluation

See Section 11 for further details. Serum PSA doubling-time (or PSA slope) response will be considered a secondary endpoint. The pre-treatment serum PSA doubling time will be calculated from four serum PSA values available from the same clinical laboratory using the same assay for the period up to one year prior to study treatment, not on other treatments for prostate cancer, up to and including the PSA value obtained at screening, using the Memorial Sloan-Kettering Cancer Center nomogram

(<http://www.mskcc.org/applications/nomograms/prostate/PsaDoublingTime.aspx>). The post-treatment PSA doubling time will be calculated using the same nomogram from:

- (1) All PSA values obtained from the same clinical laboratory using the same PSA assay beginning with the PSA value at day 1 (week 0) and continuing until the end-of study (or month 24) value (PSADT0-24).
- (2) All PSA values obtained from the same clinical laboratory using the same PSA assay beginning with the PSA value at week 12 (month 3) to the week 36 (month 9) value (PSADT3-9).

An increase in the PSA doubling time to at least double the baseline value, and at least 15 months, will be considered a PSA doubling time “response” [7].

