### C. Study Design and Sample Size Calculation

The primary efficacy endpoint is the PSA complete response (PSA  $< 0.2$  ng/mL) rate. A confirmed PSA CR will be defined as one in which serum PSA at least 4 weeks later is  $< 0.2$  ng/mL, as per PCWG2 recommendations [67]. In this patient population, the PSA CR rate is expected to be less than 5% with standard care. Hence, the null hypothesis that the PSA complete response rate is at most 5% will be tested against the alternative hypothesis that the rate is greater than 5%. A PSA complete response rate of 20% or more, on the other hand, will be considered sufficient evidence to consider further clinical trial investigation. In order to ensure sufficient accuracy in the estimation of PSA complete response, an adequate number of patients should be enrolled in this study. However, in order to avoid treating patients with a potentially ineffective therapy, a Simon optimal two-stage design with one interim analysis for efficacy will be utilized.

In the first stage, 21 patients will be enrolled and evaluated for PSA response. If a PSA complete response is observed in at most one out of the 21 patients, then study will be terminated after the first stage. Otherwise, an additional 20 patients will be enrolled in the second stage for a total of 41 patients.

Assuming that the number of subjects with a PSA complete response is binomially distributed and using a Simon-optimal two-stage design, this design has a significance of 5% and 90% power for detecting a true success (PSA complete response) probability of 20%. If the true PSA complete response rate is only 5%, the study will be terminated after the first stage with 66% probability. The expected sample size is 27 under this scenario. If, however, the true efficacy response rate is 20%, the study will be terminated early with only 6% probability with an expected sample size of 40 patients. The two-stage procedure has 98% power to detect an efficacy response rate of 25% and 71% power to detect an efficacy response rate of only 15%. The operating characteristic of the proposed balanced two-stage design are summarized in the following table:

**Table 1** *Operating characteristics of the Simon-optimal two-stage design*

True PSA complete response rate	Probability of	Power	Expected
---------------------------------	----------------	-------	----------

	early stop after stage 1		sample size
5%	66%	6%	27
10%	36%	35%	34
15%	16%	71%	38
20%	6%	90%	40
25%	2%	98%	41

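### Entry rules allow a PSA series that straddles salvage radiation, so a man whose PSA is already falling can enrol and later count as a PSA complete response

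*Combined protocol and SAP*

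**What the plan says.** Three sets of rules bear on which PSA values count.

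- **Entry.** Section 5.A item 3 requires completion of surgery and "any adjuvant/salvage radiation therapy at least 3 months prior to entry". Item 4 requires "at least 4 serum PSA measurements available, from the same clinical laboratory, at least two weeks apart up to one year", with a final value of at least 2.0 ng/mL. The entry PSADT is "calculated from most recent 4 serum PSA values (collected up to one year prior to enrollment" and need only be positive. Section 5.B item 4 adds that "Neoadjuvant/adjuvant androgen deprivation therapy administered with radiation therapy or at the time of prostatectomy is acceptable", for up to 24 months in total and without PSA progression on treatment. Section 5.B item 5 excludes a screening testosterone below 50 ng/dL.
- **Pre-treatment PSADT as an endpoint.** Section 6.B reads, in part: "PSA doubling times will be calculated from four available serum PSA values obtained up to one year from the same clinical laboratory prior to study" (the sentence goes on to end the series at the baseline value). It places no condition on earlier treatment. Section 9.C describes the same quantity but adds "not on other treatments for prostate cancer, up to and including the PSA value obtained at screening".
- **Primary endpoint.** A PSA complete response (Sections 6.B and 10.C) is a value below 0.2 ng/mL, confirmed at least 4 weeks later, without radiographic progression. Section 10.C sets the benchmark: "In this patient population, the PSA CR rate is expected to be less than 5% with standard care". The trial is single-arm.

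**The concern.** The PSA look-back is 12 months, but radiation need have ended only 3 months before entry. Up to about 9 of those 12 months can therefore precede or overlap radiation. A positive slope over such a series can reflect the rise that prompted salvage treatment, not the man's course after it. The introduction describes this disease stage as a rising PSA after definitive treatment, but the operational rule in 5.A item 4 does not secure that.

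If such a man is still declining after radiation, nothing later separates that decline from a drug effect. The response definition has no condition on earlier therapy, and there is no concurrent control. The null rate is a ceiling for standard care in this population. It is not described as covering men in post-radiation decline.

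A second, lesser issue is the pre-treatment PSADT. Values from before radiation, or from a period when testosterone is recovering after permitted androgen deprivation, may not describe the untreated PSA course against which on-study change is judged.

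**Working it through.** **1. The plan's own design figures.** Inputs from Section 10.C and Table 2: 21 patients in stage 1, stop at 1 or fewer responses; 41 in total, reject at 5 or more; null rate 5%, target 20%.

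P(reject) = Σ over x ≥ 2 of P[Bin(21, p) = x] × P[Bin(20, p) ≥ max(0, 5 − x)].

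- p = 0.20: 90.2% (stated 90%; reproduces).
- p = 0.05: 4.57%, in line with the nominal 5% and with Table 2's p = 0.046 for 5 responses.

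(The early-stop probability at p = 0.05 comes out at 71.7%, not the stated 66%. This does not affect the present point.)

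**2. Can a man with falling PSA meet 5.A item 4?** Illustrative series: 1.2, 1.6 and 2.4 ng/mL at months −11, −9 and −7; radiation from month −6 to month −4.5; 2.1 ng/mL at month −0.5.

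- PSADT = ln 2 / least-squares slope of ln(PSA) on time, the formula in Section 10.D(3).
- ln(PSA): 0.182, 0.470, 0.875, 0.742; mean 0.567. Mean time −6.875 months.
- Slope = 2.870 / 62.19 = 0.0461 per month. PSADT = 0.693 / 0.0461 = +15.0 months.
- Final value 2.1 ≥ 2.0; radiation ended 4.5 months before entry. Items 3 and 4 are met, although PSA fell from 2.4 to 2.1 across radiation.

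A second illustrative series (0.8, 1.6 and 3.2 at months −11, −8 and −5.5, then 2.0 at entry) gives +8.7 months.

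**3. How robust is the example?** The rule uses the most recent four values, so each post-radiation draw displaces an older one.

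- One extra falling draw (2.3 at month −3, or 2.2 at month −2): PSADT about +30 or +34 months. Still eligible.
- Two extra falling draws (2.4, 2.3, 2.2, 2.1 at months −7, −3, −2, −0.5): PSADT −35 months. Not eligible.

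The gap therefore concerns men with only one or two PSA values after radiation.

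**4. What one carry-over response would do.** Fix one response in advance, hold every other patient at 5%, and repeat step 1.

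| Carry-over responses | P(continue past stage 1) | P(reject null) |
|---|---|---|
| none | 28.3% | 4.6% |
| one, in stage 1 | 64.2% | 13.2% |
| one, in stage 2 | 28.3% | 10.9% |

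In Table 2, moving from 4 to 5 responses takes p from 0.114 to 0.046.

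**5. If carry-over is a rate.** Let f be the share of patients with recent radiation and q the chance that such a man reaches a confirmed value below 0.2 from the radiation alone. Both are assumptions; the documents give neither. The response rate without any drug effect becomes 0.05 + 0.95 × f × q.

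- f = 5%, q = 10%: rate 5.5%, P(reject) 6.3%.
- f = 10%, q = 10%: rate 6.0%, P(reject) 8.3%.
- f = 10%, q = 30%: rate 7.9%, P(reject) 19.2%.
- f = 20%, q = 20%: rate 8.8%, P(reject) 26.0%.

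**6. The PSADT wording.** Sections 5.A item 4 and 6.B carry no treatment condition. Section 9.C's phrase can mean that the man was off treatment at each draw, which still admits pre-radiation values. It can also mean that the whole look-back period is free of treatment, which would bar a straddling series. The text does not settle which.

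**The case against.** The strongest reply is that the route to a false response is possible but not shown to be likely. The man must still have a PSA of at least 2.0 ng/mL at least 3 months after radiation, and must then fall by at least 90% to below 0.2, with confirmation. The illustrative patient had fallen only 12.5% (2.4 to 2.1) by 4 months after radiation. Any extra response, whatever its cause, would move 4/41 to 5/41, so that arithmetic does not measure this risk. All of this stands, and it is why the effect is stated as conditional.

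It is also fair that the protocol describes its population as having a rising PSA, and that ordinary follow-up after radiation would often displace the older values. That narrows the gap but does not close it, because eligibility is decided by items 3 and 4.

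Three stronger readings are tempting, and the documents do not support them.

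- *That androgen deprivation opens a second route to a false complete response.* Recovering testosterone raises PSA, which works against a response. A castrate screening testosterone is excluded, and earlier androgen deprivation is restricted in setting and duration. What remains concerns the pre-treatment PSADT.
- *That androgen deprivation has no washout at all.* Section 5.B item 7 sets 4 weeks for other potential or experimental prostate-cancer therapies. Whether that reaches androgen deprivation is unclear, so neither reading can be asserted.
- *That the PSADT baseline is unrestricted.* Section 9.C restricts it in part. The defect is ambiguity and lack of agreement with 5.A and 6.B.

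**Conclusion.** The concern holds in a limited form. Items 3 and 4 of Section 5.A permit a qualifying PSA series that straddles salvage radiation. A man with few post-radiation draws can enter while his PSA is falling, and the response definition would not separate a later fall below 0.2 from a drug effect.

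The size for the primary endpoint is conditional on such a response occurring. One would raise the probability of rejecting a true 5% null from 4.6% to 13.2% or 10.9%, depending on stage. A reader might infer that the trial's false-positive rate is therefore 11% to 13%. That does not follow, because the documents give neither the share of recently irradiated men nor their chance of a fall of at least 90%. The rates in step 5 of the working are sensitivity values, not estimates.

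For the pre-treatment PSADT the effect is confined to a secondary endpoint, and the finding is that three definitions need reconciling.

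The change is worth making because it is cheap and removes a source of bias that a single-arm analysis cannot correct afterwards.

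**What to change.** Add to Section 5.A item 4 that all four qualifying PSA values must be drawn after completion of the most recent prostate-cancer therapy: surgery, radiation and any permitted androgen deprivation. Put the same rule in the pre-treatment PSADT definitions in Sections 6.B and 9.C, so that the three sections agree and the wording in 9.C is no longer open to two readings.

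A further requirement that the final value exceed the one before it is not advised. It would apply to every candidate. Assuming 5% to 10% PSA measurement variation and draws 2 weeks to a month apart, about 21% to 43% of men with a true 12-month PSADT would fail it by chance. The four-value slope is less exposed to that noise.

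Cost: one eligibility sentence and two aligned definitions. A small number of recently treated men may wait for further draws. Four values two weeks apart span 3 × 2 = 6 weeks, which fits within the 3 months already required after radiation. Other candidates need no added procedures.

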### (3) Analysis of Secondary Endpoints

*2-year metastasis-free Survival Rate:* The 2-year metastasis-free survival rate will be estimated using the Kaplan-Meier method and reported along with the corresponding two-sided 95% confidence interval.

*Median radiographic progression-free survival:* Radiographic progression-free survival will be estimated using the Kaplan-Meier method. The Brookmeyer-Crowley method will be used to construct the 95% confidence interval of the median radiographic progression-free survival.

*PSA doubling time:* PSA doubling time will be estimated for each patient using linear regression analysis. Specifically, PSA doubling time will be calculated as  $\log(2)$  divided by the slope parameter of the regression of  $\log(\text{PSA})$  on time. PSA doubling times and slopes will be summarized in terms of means, medians, standard deviation, and 95% confidence interval. Changes in PSA doubling time and slopes will be evaluated using a paired t-test or nonparametric Wilcoxon Signed Rank test.

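### The pre-treatment PSA doubling time must be positive for entry and may rest on four values spanning 6 weeks, so doubling time can appear to lengthen on study without any treatment effect

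*Combined protocol and SAP*

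**What the plan says.** Eligibility (5.A, item 4): the doubling time is "calculated from most recent 4 serum PSA values (collected up to one year prior to enrollment", spaced "at least 2 weeks apart, and all from the same clinical laboratory), must be a positive number". In addition, "and the final serum PSA value must be" at least 2.0 ng/mL.

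Analysis baseline: 6.B uses "four available serum PSA values obtained up to one year from the same clinical laboratory prior to study enrollment", ending with the baseline value. In 9.C, "The pre-treatment serum PSA doubling time will be calculated from four serum PSA values available from the same clinical laboratory using the same assay"; its window is again at most a year, here counted back from study treatment, and it ends with the screening value. Neither section sets a minimum span or says which four values apply when more exist.

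Use of the baseline: under 10.D(3), "Changes in PSA doubling time and slopes will be evaluated using a paired t-test" or a Wilcoxon signed rank test. Under 9.C, "An increase in the PSA doubling time to at least double the baseline value, and at least 15 months, will be considered" a doubling-time response. The post-treatment slope comes from weeks 12-36 (7 scheduled values) or from day 1 to week 96 (17 scheduled values).

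The trial has one arm (sections 6 and 10.A). No section corrects for selection on the baseline slope or for regression to the mean.

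**The concern.** A slope fitted to four PSA values a few weeks apart is mostly noise when the true rise is slow. Requiring it to be positive keeps men whose noise ran upward and drops men whose noise ran downward. Among those enrolled, the mean observed pre-treatment slope therefore exceeds the mean true slope. The on-study slope is longer, has more values and is not selected, so it falls back to the truth.

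With no control arm, that fall looks like slowing of PSA. Secondary objective 3 could then show a significant improvement, together with some doubling-time responders, under an inert treatment.

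**Working it through.** The documents give no power or error rate for the doubling-time endpoint, so there is no stated figure to reproduce.

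**Minimum span.** Four values give three gaps of at least 2 weeks: 3 x 2 = 6 weeks.

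**Precision of a four-value slope.** For equal spacing h (months), SE = SD / sqrt(5h²). With an assumed SD of ln(PSA) of 0.10:
- 6-week span: h = 2/4.333 = 0.4615; SE = 0.10 / sqrt(5 x 0.213) = 0.097 per month.
- 52-week span: h = 4; SE = 0.10 / sqrt(80) = 0.011 per month.

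A true doubling time of 12 months is a slope of ln 2 / 12 = 0.058 per month. That is smaller than the 6-week SE and about five times the 52-week SE.

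**Effect of the entry rule on one such man.** E[slope | slope > 0] = b + SE x φ(b/SE) / Φ(b/SE). At 6 weeks b/SE = 0.0578/0.0969 = 0.596, φ = 0.334 and Φ = 0.724. The expected observed slope is 0.0578 + 0.0969 x 0.461 = 0.1025, which is 1.77 times the truth. It reads as a doubling time of 0.693/0.1025 = 6.8 months instead of 12. At 52 weeks b/SE is about 5.2 and the inflation is negligible.

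**Trial-level simulation with no treatment effect.** Assumptions not in the documents:
- log-linear PSA with independent errors;
- true doubling time spread equally over 6, 9, 12, 18 and 24 months;
- SD of ln(PSA) 0.05-0.20;
- four equally spaced baseline values, with entry only if the slope is above 0;
- n = 41 and the post-treatment slope from weeks 12-36;
- least squares on log PSA, as in 10.D(3);
- paired t-test at two-sided 0.05 (10.D(3) states no level), counting only rejections toward a slower rise, so nominal 2.5%.

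| Span, same for all patients | False significant slope reduction |
|---|---|
| 6 weeks | 33-100% |
| 13 weeks | 5-83% |
| 26 weeks | 2-16% |
| 52 weeks | about 3% |

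Mixed spans fall in between. With 10/20/40/30% of patients at 6/13/26/52 weeks, the rate is about 6%, 14% and 43% at SD 0.05, 0.10 and 0.20. With 0/10/30/60% it is about 3%, 4% and 10%.

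**Doubling-time response.** For the day 1 to week 96 window, averaged over the same five doubling times, the false response rate is about 11-27% at 6 weeks and 0-5% at 52 weeks.

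**Which feature is responsible.** In a second model (median true doubling time 12 months, log-SD 0.6), dropping the positive-slope rule returns the two-sided paired-t error at a 6-week span to about 5%. For the paired test, the entry rule causes the bias and the short span magnifies it. In that model, with SD 0.10 and the entry rule kept, the mean baseline slope is overstated by 53% at 6 weeks, 14% at 12, 1.9% at 26 and 0.1% at 52.

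**The case against.** The best counter-argument concerns size. The 6-week minimum is permitted but need not be common. Section 6.A speaks of values gathered over a one-year period, which sets no minimum but suggests longer histories. A reader might infer that a false-positive result is close to certain. That needs all 41 men at the minimum span and an SD of at least 0.10, and the documents give neither the actual spans nor PSA variability. With low noise and a fast rise (SD 0.05, median doubling time 6 months) the two-sided error at 6 weeks is only about 7%. This part of the objection stands.

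A reader might also infer that most patients would be labelled responders. For an unchanged 18-month doubling time at a 6-week span the false rate is 52-63% (SD 0.10-0.20). Such a man already meets the 15-month part of the rule, however. Men with a true doubling time of 6 or 9 months contribute essentially none, and the population rate is the 11-27% above.

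Nor do the documents say that the admitting values and the baseline values are identical. Taking the most recent four is specified only for eligibility, and 6.B and 9.C differ on the last value. The two sets can coincide, and nothing prevents it.

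Finally, the endpoint carries little decision weight. The rule in 10.D(2) rests on at least 5 complete PSA responses, and section 2.G does not list doubling time among its evidence of clinical activity. That limits the consequence but does not remove it, because 10.D(3) still specifies a hypothesis test and 9.C a responder label. Section 6.B matches the post-treatment windows to a randomized trial of the vaccine alone, but no comparison with that trial is planned.

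**Conclusion.** The concern holds in conditional form. The direction of bias is certain wherever the values used for selection also enter the baseline. Its size is not known from the documents: serious if many patients have four closely spaced values or PSA is noisy relative to its rise, and negligible if spans run 6-12 months with modest noise or a fast rise. The simulated ranges rest on the assumed doubling-time mix, noise level and common span.

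Only secondary objective 3 is affected. A reader might infer that the efficacy conclusion is at risk, but the confirmed PSA complete response (below 0.2 ng/mL) does not use the baseline slope. This is an inexpensive improvement to a secondary analysis and should be made before the detailed SAP promised in 10.D(1) is written.

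**What to change.** In 6.B, 9.C and 10.D(3):
- Compute the pre-treatment doubling time and slope from all same-laboratory, same-assay PSA values in the 12 months before day 1, not from four.
- Base the change test and the response classification on patients whose values span at least 6 months.
- Report the distribution of baseline spans.
- Show the all-patient result as a sensitivity analysis, labelled as subject to regression to the mean.

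Eligibility and the primary endpoint stay as written.

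Under the same assumptions, seven values over 26 weeks give a false-positive rate of about 3-11%, and values over 52 weeks about 2-4%, against 2.5%.

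The cost is protocol and SAP wording. Some men with short PSA histories leave these analyses, and they may differ from the rest, which is why the all-patient result should be shown beside the main one. Some bias remains at a 6-month span, up to about 16% if only four values exist. The 6-month threshold is a judgement: a longer minimum removes more bias and loses more patients.
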